### [Nutrition](#)

---

The nutrition-related questions in the evaluation from 4-months postnatal up to age-5 comprise selected questions from the Child Dietary Questionnaire (CDQ), and relate to planned feeding (breast or bottle), breastfeeding, weaning age and types of foods, food supplements and dietary habits. For older children (specifically ages 5), additional questions are asked about fruit and vegetables consumption, sugar-sweetened beverages and water – three of the stronger determinants of excess weight gain in young children (as assessed from previous cohort studies). Height and weight will be measured at specific time points and mapped (for age and sex) on to standard centile charts used in the UK to assess child growth. This will give an indicator of whether a baby is under-height (stunted), underweight or overweight.

### [Domestic Violence](#)

---

Questions about domestic abuse are included in the surveys when the respondent is 26-36 weeks' pregnant and when the children are aged 1, 2, and 3 years. Respondents are asked whether they have been subject to, or used violence against their partner/ex-partner, since finding out they were pregnant, then subsequently within the last 6-months, and what type of violence this entailed (if any). These questions were adapted from Ipsos MORI/ Home Office: Violence against women and girls: teen sexual coercion, violence and rape: TRA Campaign Tracking adapted from Troubled Families evaluation.

### [Early Trauma/Abuse](#)

---

A question about whether early trauma or abuse was happening in the home when the respondent was growing up is asked at the 26-36-weeks' survey point. This question was adapted from Troubled Families evaluation.

The lengthy administration time required for the SSQ made it impractical to include the measure in full. As the consortium were unable to identify a set of questions from elsewhere that would serve a similar purpose it was decided to develop bespoke questions specifically for this survey. These bespoke questions are based on metrics measured in the SSQ, but using a standard satisfaction scale to identify participants' level of satisfaction with having people for support in each area at a general level.

These questions are included in the surveys when the children are aged 1, 2, and 3 years.

#### [Disabilities, Care and Social Worker Involvement](#)

---

Questions about whether the child, his/her parent/s or sibling/s have any learning difficulties, long-term illnesses or disabilities and any social worker involvement with the family are included in the surveys when the respondent is 26-36 weeks' pregnant and when the children are aged 1, 2, and 3 years. They were taken from the Troubled Families evaluation and Millennium Cohort Study (MCS1) Questionnaire.

<http://www.cls.ioe.ac.uk/page.aspx?&sitesectionid=860&sitesectiontitle=Questionnaire>

#### [Biological father](#)

---

Questions about the respondent's relationship with the biological father of the study child and the father's relationship with the child are included in the surveys when the respondent is 26-36 weeks' pregnant and when the children are aged 1, 2, and 3 years. They were adapted from the Millennium Cohort Study (MCS1) Questionnaire.

<http://www.cls.ioe.ac.uk/page.aspx?&sitesectionid=860&sitesectiontitle=Questionnaire>

#### [Grandparent involvement](#)

---

Questions about how often the child sees his/her grandparents and whether they help out in different ways are included in the surveys when the children are aged 1, 2, and 3 years. They were adapted from the Millennium Cohort Study (MCS1).

#### [Childcare](#)

---

Questions about which childcare arrangements the respondent uses for the study child are included when the children are aged 1, 2, and 3 years. Questions about whether the child qualifies or uses the free early years' entitlement are included at age 2 and 3 years. These are all bespoke questions.

#### [Data-linking permission and NHS number](#)

---

We will collect data from the health and social care records of the respondent and the study child using their NHS numbers. Respondents will be asked if they consent to linking their survey answers to the health and social care records of themselves and their child. This will include accessing the child's ASQ3 data – an Ages and Stages Questionnaire undertaken as part of an overall development assessment of the child at the age of 2 years.

#### [5.7.5 School-based Data Collection Measures](#)

At age 5 data will be collected from parents using a postal (or online) questionnaire administered by Ipsos MORI, rather than using face-to-face techniques.

The measures to be used are:

- Social, emotional and behavioural adjustment will be measured using the **Social Behaviour Questionnaire (age 5)**, to be completed by the child's teacher. This is an adapted version of the Strengths and Difficulties Questionnaire (SDQ), which includes selected questions from the Adaptive Social Behaviour Inventory (ASBI). See Section 3.2.1 for description of the SDQ and ASBI. The Social Behaviour Questionnaire was developed for, and validated by, the Effective Provision of Pre-School Education (EPPE) research team.

The University of Oxford will also gather administrative data from national assessments at two time-points:

- The Age 6 Phonics Check: The [phonics screening check](#) is a short, simple assessment to make sure that all pupils have learned phonic decoding to an appropriate standard by the age of 6. All year 1 pupils in maintained schools, academies and free schools must complete the check.

## 5.8 Sub-sample Protocols

Verbal consent will be taken at each time-point for each biological sub-sample. Even if a parent has consented to a previous sample, he or she can refuse consent at any time, and is under no obligation to provide a further sample. Under no circumstances will a parent be pressured into providing a sample where he or she does not wish to, and can remain in the study without providing any or further samples.

### 5.8.1 Hair Sample

Hair samples are being used in the evaluation to provide an indicator of stress by measuring cortisol levels from the mother at birth and the child aged 2 years. A trained hospital midwife will take a sub-sample of hair from the mother at birth, while the trained and experienced field researcher/interviewer will take a hair sample from the child at age 2 years. If the child does not have enough hair at either of these time-points, a sample will not be requested.

Hair strands (total diameter of approximately 3mm and total sample size of 10-50mg) will be taken from the middle of the back of the head and cut (not pulled out) with clean sterile scissors as close to the scalp as possible. It is important that the hair follicle itself is not included. The sample will then be placed in a sterile container with the scalp (root) end at the bottom.

Research and/or Community Midwives and Ipsos MORI will store hair samples at room temperature in a safe and secure area before mailing, in sealed envelopes and in batches, to the Evaluation Project Manager at the University of Warwick Medical School, where these samples will be stored before being couriered securely in batches, to the laboratory overseas for analysis. A Material Transfer Agreement will be put in place between the University of Warwick and all NHS Trusts involved in the evaluation, and with Ipsos MORI, as well as the laboratory overseas. The samples will be analysed in the lab of [name] in Germany, who leads a well-established automated laboratory for this type of analysis.

### 5.8.2 Buccal Swab

Buccal swabs are being used in the evaluation to provide epigenetic information from the baby at birth and at age-2. A trained hospital or community midwife will take a buccal (cheek) swab - from the baby at birth or in the first few weeks of life, and the trained and experienced field researcher / interviewer will take another sample again when the child is 2 years of age. A special foam tip collection swab (Epicentre catch-all collection swab) will be used. This swab comprises a long, foam bud on a plastic stick that has been specially designed for use with infants and children. The long length of the stick allows one end to be held while the other end is in the infant's mouth, eliminating any choking hazard. The foam will be gently wiped five times down the child's inner cheek. The swab will be replaced in its special Epicentre collection tube. If for any reason the infant becomes distressed, the collection will be abandoned.

Immediately after taking the Buccal Swab, Research and/or Community Midwives (at birth) and Ipsos MORI Researchers (at 2 years) will mail Buccal Swabs to the Evaluation Project Manager at the University of Warwick Medical School, where these samples will be stored in the laboratory at -20°C before being couriered securely in batches, to the laboratory overseas for analysis. A Material Transfer Agreement will be put in place between the University of Warwick and all NHS Trusts involved in the evaluation, and with Ipsos MORI, as well as the laboratory overseas. The genome-wide epigenetic profiles will be measured and analysed by [name] in the Montreal laboratory of [name], the acknowledged world leader in this type of research.

### 5.8.3 CARE Index

The CARE-Index will be used when the child is aged 1 and it has been extensively validated as a measure of parent-toddler interaction. It measures three aspects of maternal behaviour (sensitivity, covert and overt hostility, and unresponsiveness) and four aspects of a toddler's behaviour (cooperativeness, compulsive compliance, difficultness and passivity). Scores range from 0 to 14, higher scores indicating better sensitivity and/or co-operation and so on, and the scores for each are interdependent such that a high score for maternal sensitivity is related to a low score for hostility and unresponsiveness. Similarly a high score for infant co-cooperativeness is related to a low score for difficultness, passivity or compulsive compliance.

The CARE-Index has been shown to discriminate abusing, neglecting, problematic and adequate dyads. A trained and experienced Ipsos MORI field researcher and interviewer will request permission from a sub-sample of participants to take a video clip of them interacting with their child

as they would normally, for a period of 3 minutes. This video clip will be stored securely prior to being viewed only by coders who have been specially trained and certified reliable using the CARE-Index. After coding, each clip will be destroyed.

#### 5.8.4 The Manchester Child Attachment Story Task (MCAST)

The MCAST is a structured doll play methodology designed to assess young children's internal mental representations of attachment relationships with a specific caregiver. It is suitable for children aged 4-8.5 years. Using doll-play, children complete a series of attachment-related stories initiated by the researcher. The dolls represent the caregiver and the child. When compared with some other established 'story stem' measures, the MCAST is structured with a standardised script although semi-structured aspects do allow for some flexibility and adaptation for that particular child and for a more natural and engaging storytelling process.

The MCAST takes 15-30 minutes to administer and will be conducted in-school by a fully trained and experienced University of Oxford (Department of Education) field researcher. The researcher will request permission from a sub-sample of participants to undertake the MCAST with their child. The exercise will be videoed and transcribed. The video clips will be stored securely and in anonymous format prior to being viewed by the coders. Trained coders employed by the University of Oxford, Department of Education will carry out the MCAST coding. The videos will be transferred to the University Oxford using a secure password protected method.

#### 5.9 Economic Evaluation

The economic consequences of compromised outcomes in early childhood are likely to be felt across several formal sectors, including the health, social, education and voluntary sectors, as well as informal sectors. The economic evaluation will therefore focus on the following major components of costs: NHS primary and secondary care, local authority care, educational support, support from voluntary groups or other agencies, and costs borne by families and informal sectors. Intervention costs will reflect the costs necessary to implement A Better Start, including the development and training of accredited providers, the cost of delivering the programme, participant monitoring activities, and any follow-up/management.

Two economic evaluations will be undertaken: (i) a within cohort study economic evaluation will compare individual-level costs and outcomes using propensity score techniques described previously to construct the programme and comparison groups, and (ii) a decision analytic cost-effectiveness model will be used to estimate the expected incremental cost per unit change in primary outcomes for ABS in comparison to usual care. For both analyses, the economic assessment method will, as far as possible, adhere to the methodological recommendations of the NICE Reference Case (2008). The primary perspective adopted in both analyses will be that of society as a whole. However, the potential impact of adopting a NHS and personal social services perspective will also be explored in separate sensitivity analyses (NICE, 2008).

##### 5.9.1 Within Cohort Study Analysis

The within cohort study analysis will compare the costs and outcomes between *A Better Start* programme and comparison group at the end of follow up. In addition to the resource impacts associated with the delivery of A Better Start programme, broader resource utilisation will be captured through two principal sources: (i) participant questionnaires, adapted from the Client Services Receipt Inventory, administered at each follow-up point; and (ii) data from routine data collection systems. Unit costs for relevant resource inputs will largely be derived from local and national sources and estimated in line with best practice. Primary research using established accounting methods may also be required to estimate unit costs. Costs will be standardised to current prices where possible. One way of presenting the results of this economic evaluation is through the use of cost-consequences analysis, which will provide a profile of both the incremental costs and incremental consequences of A Better Start programme across relevant sectors and domains. In addition, we plan to undertake a cost-effectiveness analysis on the basis of the primary outcome measures selected for the cohort studies. Results will be presented using incremental cost-effectiveness ratios and cost-effectiveness acceptability curves generated via non-parametric bootstrapping. This accommodates sampling (or stochastic) uncertainty and varying levels of willingness to pay for reductions in the primary outcomes of interest. Additionally, net benefit statistics will be estimated. A series of sensitivity analyses will explore the effects of

uncertainty surrounding key parameters on the incremental cost-effectiveness ratios. Discounting of costs and consequences to present values will follow national methodological guidance.

#### 5.9.2 Decision Analytic Cost-effectiveness Analysis

The decision analytic cost-effectiveness analysis model will use a lifetime time horizon to capture the full impact of any differences in the primary outcomes on the long-term cost-effectiveness of A Better Start programme. The methods for estimating parameter inputs will be the same as for the within cohort study analysis, although evidence from external secondary sources (drawn for targeted literature searches) may also be required. Probabilistic sensitivity analyses will be undertaken using Monte Carlo simulation techniques. The outputs reported from this analysis will be the same as for the within cohort study analysis.

## **6. DATA MANAGEMENT**

### **6.1 Data Security**

Data security will be guaranteed by the lead organization for this tender (University of Warwick) and will comply with Department of Health (DH) /Department for Education (DfE) requirements, including the Data Protection Act. It will also comply with the University of Warwick policies, which are available as follows:

<http://www2.warwick.ac.uk/services/gov/legalservices/whentouse/dataprotection>

The University of Warwick has drawn up a Data Processing, Sharing and Transfer Agreement for the evaluation of ABS that must be signed and adhered to by all partners within the Warwick Consortium. A copy of this agreement is available on request.

For these purposes, Big Lottery Fund is the data Controller and the University of Warwick as the contractor university, is the Data Processor. The programme will be set up to ensure that all constituent members of the Management Team and extended research team are aware of and act in compliance with the data security requirements as per contract. Data security will cover data collected by the research team or commissioned researchers in addition to the data made available by the individual sites.

In particular, we will employ appropriate organisational, operational and technological processes and procedures to keep all data safe from unauthorised use or access, loss, destruction, theft or disclosure. The organisational, operational and technological processes and procedures adopted will comply with the requirements of ISO/IEC 27001 as appropriate to the services being provided to Big Lottery Fund. In all cases we will be advised and guided by the University of Warwick's Research Support Services and Data Security Officer. We will at all times comply with the Data Protection Act 1998 and comply with its requirements (e.g. all laptops have full disk encryption and all USB sticks are fully encrypted).

Data security includes the storage and protection of data from loss (e.g. appropriate back up of data on the relevant organization network and password protection). For example, data will be backed up securely and normally only be kept on a password protected networked computer. Data will not be kept on any laptop or other removable drive or device unless there is appropriate encryption and password protection, and the use of the device or laptop is necessary for the research. Laptops will have full disk encryption using either a CESG (Communications Electronic Security Group) CAPS approved product or alternatively a product that complies with the FIPS 140-2 Standard. USB devices used for transferring the Department's Data will be encrypted to the FIPS 140-2 Standard. Transmission of data between members of the team and DfE will be via encrypted and password protected files with passwords sent separately.

All the paper records (e.g. interview transcripts will be coded and hence anonymous), with codings kept separate from the written records. All material will be kept securely within locked filing cabinets. Destruction of confidential paper records will be by shredder and electronic files by the procedures advised at that time by the University'.

#### **6.1.1 Data Confidentiality**

An 'opt-in' method to the evaluation is being employed, such that at the time of potential participant identification, the participant must give consent for their name, telephone number and/or email address (only) to be passed on to Ipsos MORI in order to be contacted. For those individuals who do not provide consent, their contact details will remain confidential and will not be passed to Ipsos MORI. In these circumstances, no further action will be taken. At no time in this identification process will anyone other than the midwife and the patient have access to the patient's details, medical information or otherwise.

On recruitment of participants to the study, each individual will be allocated a unique number (i.e. the data will linked-anonymised). Ipsos MORI will keep all personal identifiers and only an anonymised dataset will be transferred securely to other members of the consortium.

The cohort survey data, and linked administrative data, will be collected by Ipsos MORI but primarily analysed by Drs [name] and [name] of Bryson Purdon Social Research LLP (BPSR).

Non-identifiable data only that is generated from the study will be stored securely, in a format that can be analysed (i.e. SPSS files), in accordance with Data Protection procedures, by Big Lottery Fund as Data Controller for the study. This includes coded non-identifiable data files generated from the additional CARE-Index and Story-stem subsamples. All films will be deleted from the video camera as soon as they are downloaded on to a disc to be coded. Once coded, these discs will be securely and professionally shredded by the Universities of Warwick (CARE index) and Oxford (Story-stem).

Samples of hair and buccal swabs will be kept by the relevant laboratories and will not be used for any further research purposes without the further consent being sought from the participating families. Data confidentiality will be secured using unique number coding, thus samples will be non-identifiable.

## 6.2 Data Analysis

The baseline and cohort studies are complex and cover a very large range of outcomes, over multiple data collection points. The longitudinal cohorts will generate a steady stream of rich and complex data the analysis of which is to be planned in detail before each analysis stage. A balance will need to be struck between exploring the data in depth, so that the data contribute as much as possible to our understanding of the nature and size of programme effects, and contributes to the evaluation in a formative way, but without any risk of 'fishing' for positive results. We plan to manage this as follows:

At the start of each analysis phase, and before any data analysis has started, the team will generate a detailed analysis plan. This will cover:

1. The outcomes to be included in the analysis, including how they are to be coded;
2. The datasets to compare (e.g. whether the analysis will compare newly created datasets with earlier ones from the evaluation (including the baseline), or whether the comparison will be cross-sectional programme v comparison);
3. Whether there are to be any sub-groups analyses;
4. How 'explanatory' variables are to be used;
5. How the analysis will be done (such as when, and how, propensity score matching will be used, regression analysis, and so on);
6. How to present the results (i.e. tables, graphs etc.)

The decisions on the analysis plan each time will partly be driven by programme theory (that is, what changes might we expect to observe, given the logic of the programme). But there will also be new hypotheses to be tested, these being generated by other strands of the evaluation (such as any suggestions from the implementation study that the programme is looking to be particularly successful for some groups of parents and less so for others).

Over and above this planned analysis, we will include some exploratory analysis at each phase – such as running impact estimates for a range of sub-groups over and above the sub-groups for which theory suggests that differences should arise. This analysis will be kept separate from the main analysis, and reported on as separate. The intention is to use the data to identify any potential anomalies in impacts that can then be fed back into the implementation study for testing.

As data build up from the longitudinal study we will start to create multiple datasets that can then be analysed in multiple ways. Much of the analysis will be child-age-specific and will use the data cross-sectionally. For instance, when looking at the impact of the programme by age 3, comparisons will be made across six independent samples: baseline, cohort 1, and cohort 2, in both programme and comparison areas. The sorts of questions this will answer will be whether change since baseline in age 3 outcomes has been greater in programme areas than in comparison areas. Other analyses will make more direct use of the longitudinal nature of the two cohorts: such as 'have children in programme areas followed different trajectories over their early years than children in comparison areas'. Or, 'to what degree can outcomes at age 3 be explained by earlier experiences of the parent and child'.

We envisage that most of our analysis of impact will be based on comparisons between programme and comparison area groups that have been balanced on confounding variables using propensity score matching. That is, each time the comparison area data is used to generate an estimate of the counterfactual, differences between the background characteristics of the two groups (programme and comparison) will be established using regression modelling (either probit or logistic regression)

and a 'propensity' to be in the programme group estimated. The two groups will then be matched on this propensity score. This will ensure a reasonably close match in the two groups on the full range of background characteristics. If there is evidence of biasing non-response effects in the cohorts over time then weighting of the data to try and remove any such bias will be considered. All statistical tests and standard errors will be calculated taking into account the matching, non-response weights, and between-comparison-area effects.

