Big Lottery Fund has invested in the Warwick Consortium, led by the University of Warwick, to conduct a 10-year study designed to evaluate the impact of ABS across these five selected intervention areas, compared with matched comparison sites.

In addition to the impact evaluation, Warwick Consortium are also undertaking an implementation evaluation involving the collection of process data from the participating sites, and a learning and dissemination work-stream to ensure that the lessons in terms of what works, for whom, and why, are identified and widely disseminated.

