### 5.1.2 Areas and Timelines

During the baseline survey (2016/17) and cohort study (January 2019 - 2026), data will be collected from:

- 5 intervention areas
  - **Blackpool** (wards: Brunswick; Talbot; Claremont; Bloomfield; Clifton; Park; Victoria);
  - **Bradford** (wards: Bradford Moor; Little Horton; Bowling & Barkerend);
  - **Lambeth** (wards: Stockwell; Tulse Hill; Vassall; Coldharbour);
  - **Nottingham** (wards: Arboretum; St Anne's; Bulwell; Aspley);
  - **Southend** (wards: Milton; West Shoebury; Westborough; Shoeburyness; Victoria; Kursaal)
- 13 comparison areas (3 per programme area):
  - BLACKPOOL COMPARATORS**
    - **Barnsley** (wards: North East; Stairfoot; Dearne South; Worsbrough; Monk Bretton; St Helens; Dearne North)
    - **Stoke-on-Trent** (wards: Joiner's Square; Burslem Central; Blurton West & Newstead; Meir South; Hollybush & Longton West; Meir North; Bentilee & Ubbertley)
    - **Plymouth** (wards: Moor View; Efford & Lipson; St Duseaux; Ham; Devonport; St Peter & the Waterfront; Honicknowle)
  - BRADFORD COMPARATORS**
    - **Coventry** (wards: Binley & Willenhall; Foleshill; Longford)
    - **Derby** (wards: Sinfin; Normanton; Arboretum)
  - LAMBETH COMPARATORS**
    - **Islington** (wards: Junction; Tollington; Hillrise; Holloway)
    - **Hackney** (wards: Cazenove; Lordship; Queensbridge; Stoke Newington Central)
    - **Hammersmith and Fulham** (wards: Askew; Shepherd's Bush Green; College Park & Old Oak; Wormholt & White City)
  - NOTTINGHAM COMPARATORS**
    - **Hull** (wards: Bransholme East; Ings; Newington; Pickering)
    - **Southampton** (wards: Bevois; Coxford; Redbridge; Bitterne)
    - **Birmingham** (wards: Billesley; Kings Norton; Bartley Green; Springfield)
  - SOUTHEND COMPARATORS**
    - **Sefton** (wards: Cambridge; Duke's; Ford; Kew; Netherton & Orrell; Norwood)
    - **Portsmouth** (wards: Hilsea; Fratton; Cosham; Nelson; Paulsgrove; Charles Dickens)

Table 1 provides both an overview of data collection methods at each study time-point, and of the timeline for both the baseline and cohort studies.

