### 5.5.2 Main Cohort Evaluation Surveys

The primary research question will be addressed using a longitudinal cohort study in which a target of 2,885 pregnant women across the five intervention and fifteen matched comparison areas will be recruited to the study. Further detail is provided in Table 2.

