### 5.5.3 Sample Size Justification

The sample size for the cohort study has been set with the primary aim, after attrition, of generating 815 interviews with parents of three year olds in programme areas and 555 in comparison areas. The 'headline' estimates of impact will be based on difference-in-differences estimates. That is, change since baseline for children of the same age group in ABS areas, minus change since baseline in comparison areas. For outcomes at age 1, for instance, this will be based on the four sets of data within the second row of the table (i.e. 500; 270; 1200; 825). Samples of this size will enable detection of effect sizes of 0.25 standard deviations (with 80% power). For binary outcomes, this equates to being able to detect an impact of around 12 percentage points (i.e. if 12% of children in ABS areas have a better outcome at age 1 as a direct result of the programme, a difference-in-difference estimate should be observed that is significantly different to zero). At Age 2 the cohort sample sizes will have been subject to attrition, and the detectable effect size at age 2 will be just over 0.25; and with further attrition at Age 3, the detectable effect size will be 0.26.

In practice, it is hoped that no real differences in the baseline outcomes for ABS and comparison areas will be observed. If baseline differences can be ruled out, then the evaluation can focus on comparing the ABS and comparison cohort samples. This will greatly improve the statistical power. For example, at age 1, if only the two cohort samples of 1200 and 825 were compared, effect sizes of 0.13 standard deviations could be detected.

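### The stated detectable effects contain no area effect, contrary to the analysis in section 6.2, and section 6.2 names area variance only for the comparison areas, not for the five programme areas

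*Protocol*

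**What the plan says.** Section 2.1 sets the aim: "evaluate the impact of ABS across these five selected intervention areas, compared with matched comparison sites". The programme is therefore assigned by area, and the programme side has five of them.

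Section 5.5.3 makes DiD the headline method ("estimates of impact will be based on difference-in-differences estimates"). For age 1 it uses baseline samples of 500 and 270 and cohort samples of 1200 and 825, and concludes: "Samples of this size will enable detection of effect sizes of 0.25 standard deviations (with 80% power"). It gives just over 0.25 at age 2 and 0.26 at age 3. If baseline differences can be ruled out, it allows a comparison of the two cohort samples alone, for which "effect sizes of 0.13 standard deviations could be detected" at age 1. The section mentions no ICC, design effect or number of areas.

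Section 6.2 says what the standard errors will contain: "All statistical tests and standard errors will be calculated taking into account the matching, non-response weights, and between-comparison-area effects". Neither section names variation between programme areas, or variation within an area from baseline to cohort.

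The number of comparison areas is inconsistent. Section 5.1.2 announces "13 comparison areas (3 per programme area") and lists 13, with two each for Bradford and Southend. Section 5.5.2 speaks of "five intervention and fifteen matched comparison areas", and sections 5.5.1 and 5.5.4 also say fifteen.

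**The concern.** There are two linked problems.

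First, the power statement and the planned analysis do not match. If the standard errors carry matching, weights and comparison-area effects, the detectable effects must carry them too. Otherwise the stated 80% power belongs to an analysis that will not be run.

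Second, the one area term that is named is the smaller one. Local changes unrelated to ABS affect programme areas as well as comparison areas. With equally variable areas of equal size, the area component enters the estimate as 1/5 on the programme side and 1/13 on the comparison side. A standard error holding only the comparison-area term is too small, its intervals are too narrow, and the test rejects too often. Recruiting more families does not shrink this component; the number of areas limits it.

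At stake is whether a local shift in a few areas could be reported as a significant programme effect, and whether a true effect near the stated detectable size is likely to be found.

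**Working it through.** **Inputs.** Sample sizes come from section 5.5.3 and Table 2. There are five programme areas, and 13 comparison areas as listed in section 5.1.2. Assumed: two-sided 5% (not stated, but it reproduces the plan's figures), SD 1, and equal-sized areas. The ICC is also assumed, at 0.005, 0.01 and 0.02. So is the correlation r of an area's effect between baseline and cohort, at 0.5.

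**Step 1: reproduce the plan's figures.** For independent individuals, MDE = (1.960 + 0.842) × √(sum of 1/n).

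| Comparison | n | SE | MDE | Stated |
|---|---|---|---|---|
| DiD age 1 | 500, 270, 1200, 825 | 0.0880 | 0.247 | 0.25 |
| DiD age 2 | 500, 270, 1060, 720 | 0.0896 | 0.251 | just over 0.25 |
| DiD age 3 | 500, 270, 815, 555 | 0.0934 | 0.262 | 0.26 |
| Cohort-only age 1 | 1200, 825 | 0.0452 | 0.127 | 0.13 |

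All four match with a design effect of 1. The largest design effect that still rounds to the stated value is (0.255/0.247)² ≈ 1.07 for the age-1 DiD and (0.135/0.127)² ≈ 1.14 for cohort-only (unrounded MDEs used). With 1200/5 = 240 children per programme area, ICC 0.01 alone gives 1 + 239 × 0.01 = 3.4 on the programme side of the cohort-only comparison. That the stated figures contain no area effect needs no assumed ICC.

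**Step 2: headline DiD at age 1 with area variance.**
Full variance = 2 × ICC × (1 − r) × (1/5 + 1/13) + (1 − ICC) × (sum of 1/n). The comparison-only variance keeps 1/13 and drops 1/5. True type I error = 2 × [1 − Φ(1.96 × SE comparison-only / SE full)].

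For ICC 0.01 and r = 0.5, the full variance is 0.01 × 0.2769 + 0.99 × 0.007749 = 0.01044, so the SE is 0.1022 and the MDE 0.286. The comparison-only SE is 0.0919, a ratio of 0.899, which gives a type I error of 7.8%.

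| ICC | MDE | Power at 0.25 SD | Type I error, comparison-area term only |
|---|---|---|---|
| 0 | 0.247 | 81% | 5% |
| 0.005 | 0.267 | 75% | 6.4% |
| 0.01 | 0.286 | 69% | 7.8% |
| 0.02 | 0.321 | 59% | 10.2% |

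Sensitivity to r at ICC 0.01: power at 0.25 SD is 59% for r = 0 and 76% for r = 0.8. Using t on 5 + 13 − 2 = 16 df, the MDEs at r = 0.5 become 0.285, 0.305 and 0.342.

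**Step 3: conditional cohort-only comparison at age 1.**
Full variance = ICC × (1/5 + 1/13) + (1 − ICC) × (1/1200 + 1/825).

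| ICC | MDE | Power at 0.13 SD | Type I error, comparison-area term only |
|---|---|---|---|
| 0 | 0.127 | 82% | 5% |
| 0.001 | 0.135 | 77% | 6.1% |
| 0.002 | 0.143 | – | 7.1% |
| 0.005 | 0.164 | 60% | 10% |
| 0.01 | 0.194 | 47% | 13% |
| 0.02 | 0.243 | 32% | 18% |

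With fifteen comparison areas instead of 13, the MDEs move by at most about 0.01, because the 1/5 term dominates. No matching or weighting design effect is included, since the protocol gives no basis for one; it would raise these figures further.

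**The case against.** **The five areas are fixed.** The aim concerns these five selected areas, not a sample of areas, so treating them as fixed and the comparison areas as sampled is a recognisable choice that fits section 6.2. It does not rescue the figures. Local shocks in the five areas remain in the estimated difference and cannot be told apart from programme effect. Even with the comparison-area term alone, the cohort-only MDE is 0.138, 0.148 and 0.167 for ICC 0.005, 0.01 and 0.02, and the age-1 DiD MDE is 0.252, 0.257 and 0.268.

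**The detail is left to later plans.** Section 6.2 requires an analysis plan before each phase, and its list of what the standard errors reflect is not said to be exhaustive. A reader might infer that programme-area variance is ruled out; the text does not say so. The inflated type I error is therefore conditional on the wording being applied as it stands. The power figures, however, are stated in the protocol itself and disagree with it.

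**DiD and matching reduce the problem.** This stands in part. DiD removes stable area differences and leaves area-by-period variation. Areas are matched on seven indicators and families on propensity scores, so the residual ICC may be small; at 0.001 to 0.002 the cohort-only type I error is 6% to 7%. A reader might carry the 10% to 18% rates over to the headline analysis. They belong only to the conditional cohort-only comparison.

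**Age 3.** A reader might recompute the age-3 DiD with the section 5.5.1 baselines (208 and 216), obtain about 0.35 at ICC 0.01 and r = 0.5, and blame area effects for the whole rise from 0.26. Those baselines give 0.313 with no area effect at all. With the section 5.5.3 baselines and the same area term the result is about 0.30. Most of the rise reflects a separate mismatch in baseline sizes.

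**Area count.** A reader might infer that fifteen is simply an error for 13. The documents do not settle it: section 5.5.1 places baseline interviews in all fifteen, and section 5.5.4 names a pilot area, East Kent, that is absent from the section 5.1.2 list.

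**Conclusion.** The point holds as a mismatch between sections 5.5.3 and 6.2 and as an incomplete variance statement in section 6.2. The first part follows from the document's own figures. The direction of the second holds for any non-zero area variance (area-by-period variance for DiD), including in the programme areas. Its size is not established by the documents, because it depends on an assumed ICC and between-period correlation.

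Over ICC 0.005 to 0.02 with r = 0.5, the headline age-1 DiD loses a moderate amount: power at 0.25 SD falls from 81% to between 75% and 59%, and type I error is 6% to 10% if only the comparison-area term is used. The cohort-only option, which section 5.5.3 presents as a large gain in power, is much more exposed: its 0.13 SD becomes 0.16 to 0.24 over the same range. The disagreement over the number of comparison areas is editorial, with little numerical effect.

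**What to change.** 1. **Section 6.2:** state that standard errors will reflect between-area variation (area-by-period variation for DiD) in both programme and comparison areas, with a correction for the small number of areas, such as t on about 16 df or permutation across areas.
2. **Section 5.5.3:** restate the detectable effects over a stated ICC range, for example 0.005 to 0.02, with a design effect for matching and weighting. Failing that, say plainly that the present figures assume no area effect and are best case.
3. **Sections 5.1.2, 5.5.1, 5.5.2 and 5.5.4:** reconcile the number of comparison areas and use the reconciled number in the recalculation.

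The cost is revised wording and a recalculated table. The downside is wider intervals and less favourable stated detectable effects.
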